**Contraindications (all answers have to be no):**

- Hypersensitivity to the active substance or to any of the excipients (yes/no)
- Infection with human immunodeficiency virus (HIV) (yes/no)
- Active chronic infection (tuberculosis or hepatitis) (yes/no)
- Initiation of cladribine treatment in immunocompromised patients, including patients currently receiving immunosuppressive or myelosuppressive therapy (yes/no)
- Active malignancy (yes/no)
- Moderate or severe renal impairment (creatinine clearance <60 mL/min) (yes/no)
- Pregnancy and breast-feeding (yes/no)

**Recommended screening for infections (all answers have to be yes)** - A delay in initiation of Cladribine 10 mg tablets should also be considered in patients with an acute infection until the infection is fully controlled.

- Active or latent tuberculosis excluded (yes/no)
- Active infection with hepatitis B virus (HBV) excluded (yes/no)
- Active infection with hepatitis C (HCV) excluded (yes/no)

**Vaccination – If vaccination is needed, initiation of treatment with Cladribine 10 mg tablets must be postponed for 4 to 6 weeks to allow for the full effect of vaccination to occur**

- Vaccination with live or attenuated live vaccines within 4–6 weeks before initiation of Cladribine 10 mg tablets (yes/no)

**Pregnancy and contraception (all answers have to be yes)**

- Pregnancy excluded in women of childbearing potential (yes/no)
- Women of childbearing potential must agree to prevent pregnancy by use of effective contraception during Cladribine 10 mg tablets treatment and for at least 6 months after the last dose. Women using systemically acting hormonal contraceptives should add a barrier method during Cladribine 10 mg tablets treatment and for at least 4 weeks after the last dose in each treatment year. Women who become pregnant under therapy with Cladribine 10 mg tablets should discontinue treatment. (yes/no)
- Male patients must agree to take precautions to prevent pregnancy of their partner during Cladribine 10 mg tablets treatment and for at least 6 months after the last dose. (yes/no)

**Assessment before therapy initiation (all answers have to be yes)**

- Lymphocyte count must be at least 800 cells/mm^3 before initiating Cladribine 10 mg tablets in year 2
- MRI should be performed before continuing Cladribine 10 mg tablets to exclude PML (within 3 months)
- MRI status
- EDSS score
- Patient weight
- Lymphocyte count
- Number of Cladribine 10 mg tablets to be used in the whole treatment course year 2
- Any relapse and rescue therapy from the last visit
- Any AE from the last visit
- Concomitant medication (only corticosteroids, myorelaxants, analgesics, antidepressants, anxiolytics) from the last visit

**V5 - Visit Month 3 Year 2** (2 months after the first dose of Cladribine 10 mg tablets in Year 2)

- Visit date
- Date of Cladribine 10 mg tablet therapy start
- Number of Cladribine 10 mg tablets really used in the whole treatment course year 2
- Lymphocyte count
- Any relapse and rescue therapy from the last visit
- Any AE from the last visit
- Concomitant medication (only corticosteroids, myorelaxants, analgesics, antidepressants, anxiolytics) from the last visit

**V6 - Visit Month 7 Year 2** (6 months after the first dose of Cladribine 10 mg tablets in Year 2)

- Visit date
- Lymphocyte count
- EDSS score
- Any relapse and rescue therapy from the last visit
- Any AE from the last visit

- Concomitant medication (only corticosteroids, myorelaxants, analgesics, antidepressants, anxiolytics) from the last visit

**V7 - Visit Month 12 Year 2/Month 1 Year 3** (12 months after the first dose of Cladribine 10 mg tablets in Year 2)

- Visit date
- MRI status
- EDSS score
- Any relapse and rescue therapy from the last visit
- Any AE from the last visit
- Concomitant medication (only corticosteroids, myorelaxants, analgesics, antidepressants, anxiolytics) from the last visit

**V8 - Visit Month 7 Year 3** (18 months after the first dose of Cladribine 10 mg tablets in Year 2)

- Visit date
- EDSS score
- Any relapse and rescue therapy from the last visit
- Any AE from the last visit
- Concomitant medication (only corticosteroids, myorelaxants, analgesics, antidepressants, anxiolytics) from the last visit

**V9 - Visit Month 12 Year 3/Month 1 Year 4** (24 months after the first dose of Cladribine 10 mg tablets in Year 2)

- Visit date
- MRI status
- EDSS score
- Any relapse and rescue therapy from the last visit
- Any AE from the last visit
- Concomitant medication (only corticosteroids, myorelaxants, analgesics, antidepressants, anxiolytics) from the last visit

**V10 - Visit Month 7 Year 4** (30 months after the first dose of Cladribine 10 mg tablets in Year 2)

- Visit date
- EDSS score
- Any relapse and rescue therapy from the last visit
- Any AE from the last visit
- Concomitant medication (only corticosteroids, myorelaxants, analgesics, antidepressants, anxiolytics) from the last visit

**EOS - Visit Month 12 Year 4** (36 months after the first dose of Cladribine 10 mg tablets in Year 2)/Premature Withdrawal Visit

- Visit date
- MRI status
- EDSS score
- Any relapse and rescue therapy from the last visit
- Any AE from the last visit

Concomitant medication (only corticosteroids, myorelaxants, analgesics, antidepressants, anxiolytics) from the last visit

Table 8-1: Flow chart

Year	Year 1			Year 2			Year 3		Year 4		
	pre-dose	3	7	pre-dose	3	7	1	7	1	7	12
Timing (month if applicable)	V1	V2	V3	V4	V5	V6	V7	V8	V9	V10	EOS /PW*
Informed consent	X										
Inclusion/Exclusion criteria	X										
Baseline characteristics (patient and disease)	X										
Patient weight	X			X							
Is patient eligible to start Cladribine 10 mg tablets therapy?	X			X							
MRI status	X			X			X		X		X
Lymphocyte count (or Blood count)	X	X	X	X	X	X					
Number of Cladribine 10 mg tablets to be used	X			X							
Date of Cladribine 10 mg tablet therapy start and number of Cladribine 10 mg tablets really used (as counted from original packages brought back to the site)		X			X						
EDSS	X		X	X		X	X	X	X	X	X
Any relapse and rescue therapy from the last visit		X	X	X	X	X	X	X	X	X	X
Any AE from the last visit		X	X	X	X	X	X	X	X	X	X
Concomitant medication (only corticosteroids, myorelaxants, analgesics, antidepressants, anxiolytics) from the last visit		X	X	X	X	X	X	X	X	X	X
Reasons for premature withdrawal, if applicable											X

\*PW – Premature Withdrawal Visit in case of patient premature withdrawal

### **8.3 Lost to follow-up patients**

If a patient is lost to follow-up (they fail to appear for visits without stating an intention to discontinue or withdraw), the site will attempt to communicate with the patient. Sites will be requested to spare no effort in contacting patients at various times of the day and evening, and on different days of the week to verify health status of a patient.

## **9 DATA MANAGEMENT**

### **9.1 Data Capture**

The participating physician will fill all required data in the eCRFs for each patient anonymously within 10 working days from performed relevant visit. Only the participating physician will be able to identify the patient in question.

Prior to granting access to the eCRF, the physician will be trained. Instructions for filling in the eCRF will be provided in a separate document.

The participating physician will ensure that the information contained in patient records is complete, accurate and correct.

### **9.2 Site and Patient Numbering**

Project Data Management will assign a specific number to each centre and a unique identification number to each patient. All participating sites will only have access to view and enter the data for their own patients.

### **9.3 Data Validation**

Data processing may open additional questions to which the participating physician is required to respond by confirming or modifying the data. Response questions will be attached to records that will be archived by the participating physician and the Sponsor.

The procedures for data collection and validation will be detailed in the relevant working documents.

## **10 QUALITY CONTROL AND QUALITY ASSURANCE**

Quality Assurance representative(s) of Sponsor (or their designee) may conduct audit visits at any time during the study period. All necessary related data and documents will be made available for inspection.

### **10.1 Site Training and Initiation**

A meeting will be held to train the Investigators (participating physicians) and their site staff on the study requirements and use of the eCRF. Sponsor (or their designee) will contact each site to review site initiation procedures. Ongoing site management will occur throughout the entire duration of the study. Additional outreach and training including on-site visits will occur for sites (Investigators and staff) needing remedial training and to address quality control concerns prior to analysis.

### **10.2 Site Monitoring**

In-house site management and site monitoring will be used to manage sites during the study

conduct. Random control of data quality will be performed at minimum 10% of active sites with at least one enrolled patient. Records will be checked for data completeness and accuracy by qualified Sponsor representative (or their designee) who will have access to all medical records, the investigator's trial-related files and correspondence, and the informed consent documentation of this study.

If specific problems are identified in some centres, the percentages of quality control checks in a given centre will be appropriately increased and corrective actions will be taken.

## 11 PHARMACOVIGILANCE

Physicians have to collect all adverse events during the whole study – from the Visit V1 - Pre-dose Year 1 to the EOS/PW without regard to their severity or relationship with Cladribine 10 mg tablets and record them (including follow-up information if applicable) in the respective eCRFs. Reports of Special Situations (see definition bellow) are also to be recorded in the eCRFs following the AE procedure, even if occurring without AE.

Physician has to take all appropriate measures to ensure patient safety as per standard of care. Treatment of any adverse event is left at discretion of the physician who has to follow Cladribine 10 mg tablets SmPC and standard clinical practice.

### 11.1 Definitions

**An Adverse Event (AE)** is any untoward medical occurrence in a patient or clinical study subject administered a pharmaceutical product and which does not necessarily have a causal relationship with this treatment. An AE can therefore be any unfavourable and unintended sign (including an abnormal laboratory finding), symptom, or disease temporally associated with the use of a medicinal product, whether or not considered related to the medicinal product.

**An Adverse Reaction (AR)** is a response to a medicinal product which is noxious and unintended. Response in this context means that a causal relationship between a medicinal product and an AE is at least a reasonable possibility.

ARs may arise from use of the product within or outside the terms of the marketing authorization or from occupational exposure. Conditions of use outside the marketing authorization include **Special Situations** as following:

- Use of a medicinal product during pregnancy or breastfeeding: reports where embryo, foetus or child may have been exposed to medicinal products (either through maternal exposure or transmission of a medicinal product via semen following paternal exposure);
- Reports of overdose, abuse, off-label use, misuse, medication error or occupational exposure;
- Lack of therapeutic efficacy;
- Prescription error/dispensing error, e.g., due to confusion of invented names of the medicinal products;
- Drug interaction;
- Suspected transmission of an infectious agent via a medicinal product; or
- Product complaints (incl. falsified products or counterfeit products).

Special Situations will be considered in the Final Study Report or any interim reports, as applicable.

**A Serious Adverse Event (“SAE”)/Serious Adverse Reaction (“SAR”)** is any AE/AR as defined above, which also fulfils at least one of the seriousness criteria below:

- results in death,

- is life-threatening,
- requires in-patient hospitalization or prolongation of existing hospitalization,
- results in persistent or significant disability/ incapacity,
- is a congenital anomaly/ birth defect, or
- is otherwise considered as medically important.

1) Life-threatening in this context refers to a reaction in which the patient was at risk of death at the time of the reaction; it does not refer to a reaction that hypothetically might have caused death if more severe.

2) Medical and scientific judgement should be exercised in deciding whether other situations should be considered serious reactions, such as important medical events that might not be immediately life threatening or result in death or hospitalisation but might jeopardise the patient or might require intervention to prevent one of the other outcomes listed above. Examples of such events are intensive treatment in an emergency room or at home for allergic bronchospasm, blood dyscrasias or convulsions that do not result in hospitalisation or development of dependency or abuse.

*Note: Event term 'Death', 'Disability' and 'Hospitalization'*

Death, disability, and hospitalization are considered outcomes in the context of safety reporting and not usually considered ARs/AEs. Therefore, the primary cause of death, disability or hospitalization should be recorded and reported as an SAE/AR, and the outcome should be recorded in a separate data field. However, a term for the outcome will be selected if it is the only information reported or provides significant clinical information.

If death occurs, the primary cause of death or event leading to death should be recorded and reported as an SAE. "Fatal" will be recorded as the OUTCOME of this respective event and not be as separate event. Only, if no cause of death can be reported (for example, sudden death, unexplained death), the death per se might then be reported as an SAE.

**Adverse Events of Special Interest (AESI)** are those events thought to be potentially associated with Cladribine 10 mg tablets or disease under study. Reporting on Adverse Events of Special Interest is an emerging and ever more critical aspect related to characterizing the safety profile of a compound.

In this study AESIs are:

- Lymphocyte toxicity grade 3 and 4 per CTCAE
- Herpes zoster infection
- Malignancy

**Events NOT to be considered AEs in this study:**

- Medical conditions present in a patient and documented at the time of enrolment of the Non-Interventional Study, and that do not worsen in severity or frequency during the Non-Interventional Study, are defined as baseline medical conditions, and are NOT to be considered AE.
- Symptoms and signs of relapse or worsening of MS will usually be captured in the context of the efficacy assessment and recorded on the relapse module of the eCRF. Therefore, symptoms, relapses or worsening of MS will not be considered as AEs nor captured on the AE module of the eCRF unless considered possibly or probably related to the Cladribine 10 mg tablets (i.e. worsening is not consistent with the anticipated natural progression of the disease).
- Progression of the disease/disorder being studied assessed by measurement of lesions on radiographs or other methods as well as associated clinical signs or symptoms (including laboratory abnormalities) should not be reported as an (S)AE, unless the

subjects' general condition is more severe than expected for the participant's condition and/or unless the outcome is fatal within the AE reporting period (from ICF signature to the last study visit).

#### **AE Severity and Causality Assessment:**

Physicians should assess the severity/intensity of any AE as follows:

- **Mild:** The subject is aware of the event or symptom, but the event or symptom is easily tolerated.
- **Moderate:** The subject experiences sufficient discomfort to interfere with or reduce his other usual level of activity.
- **Severe:** Significant impairment of functioning: the subject is unable to carry out usual activities.

Physicians must assess the causal relationship between AEs and study drug considering temporal relationship between the AE onset and study drug administration, safety profile of study drug (known ARs), the patient's condition (medical history, underlying disease), concomitant medication, and study procedures.

- **Related:** Suspected to be reasonably related to any study medication.
- **Not related:** Not suspected to be reasonably related to any study medication. A reasonable alternative explanation must be provided.

## **11.22. Recording and Transmission of Safety Events**

### **11.2.1 Responsibilities**

Participating physicians will be responsible for the recording and handling of safety information, including, without limitation, AEs and ARs reported as part of the study, including a causality assessment. Participating physician shall ensure that information on any AE is recorded comprehensively and in high quality. Marketing authorization holder (MAH) of the Cladribine 10 mg tablets shall be responsible for the regulatory reporting of safety events to competent health authorities in accordance with Applicable Laws and Codes.

Participating physicians shall comply with the adverse event reporting and safety data exchange requirements set forth in protocol sections 11.2.2 and 11.2.3 bellow and any other such obligation required by Applicable Laws and Codes. ARs related to pharmaceutical products other than the Cladribine 10 mg tablets should be notified to the respective marketing authorization holder or competent health authorities in accordance with Applicable Laws and Codes.

Participating physicians shall fully cooperate with Cladribine 10 mg tablets MAH to enable MAH to meet its safety-related reporting obligations in relation to events or findings associated with the study, inter alia by providing comprehensive, high quality information and support in the follow-up on any safety data.

### **11.2.2 Safety Events Reporting**

For recording in the safety data base, all SAEs (related and non-related, including all fatal outcomes), related non-serious AEs\* (ARs), AESIs, Special Situations and other safety events not classified under any of the above mentioned categories which might be emerging safety issues shall be sent to MAH in English language. The information shall be sent via facsimile or email listed below within one (1) business day or three (3) calendar days, whatever comes first, after becoming aware of the event. Contact details are as follows:

- [name]

- [contact]

It is recommended to use MAH's safety data collection forms for non-interventional studies.

\* Non-serious AR reports shall be sent within four (4) calendar days via individual report form or in agreed alternative way.

Once an adverse event is detected, it must be followed until its resolution or until it is judged to be permanent (e.g. Continuing at the end of the study).

The data entered on the safety data collection forms must be consistent with the information recorded in the eCRFs. If some data are missing, the form should be completed with the available data and a follow-up report should be sent as soon as possible. The minimum information to be included in the initial report is the following:

- Investigator name and contact details
- Subject identification (e.g., ID number, gender, age)
- Product (including lot/ batch number)
- Description of SAE/AR/ fatal case/ Special situation

The report should contain causality and seriousness information (for AEs) and must be signed off by the physician.

All follow-up information for the AEs including information on complications, progression of the initial AE and recurrent episodes must be reported as follow-up to the original episode within the timeframe applicable to the event category as specified above. An AE occurring at a different time interval or otherwise considered completely unrelated to a previously reported one must be reported separately as a new event.

After submission of the initial report, participating physician and/or Coordinating Investigator may be contacted by the drug safety department of MAH or the study Data Management to obtain follow-up or additional information on the event or for data clarification. Participating physician and/or Coordinating Investigator shall make best effort to obtain the requested information.

MAH will perform a company medical assessment for the purpose of signal detection and cumulative reporting of safety information.

MAH of the Cladribine 10 mg tablets is responsible to report all suspected adverse drug reactions and individual case safety reports for expedited reporting arising in the study to the competent health authorities in accordance with Applicable Laws and Codes.

Safety data will be coded by using the MedDRA Coding Terminology in study database by authorized CRO.

MAH will perform regular signal detection on the Cladribine 10 mg tablets in its global safety database. In case of any action arising from such signal detection activities which is relevant for the conduct of the study, MAH will inform participating physicians and Coordinating Investigator in a timely manner.

As part of the monthly reporting, participating physician shall provide MAH with a monthly list of all safety reports, sent to MAH in order to verify that MAH has received all reported cases. MAH will timely check the list and request missing cases, if any.

MAH shall be responsible for compilation and submission to competent authorities of all periodic safety update reports in accordance with Applicable Laws and Codes.

Complete data on AEs (including Special Situations) shall be collected and provided to MAH at the end of the study as part of the final study report, or during the course of the study upon special written request by MAH. All safety data sets shall be provided in an internationally accepted format which allows integration into the global clinical database for the product of MAH.

### 11.2.3 Reporting of Pregnancies in the Study

In case of pregnancy, physician has to follow Cladribine 10 mg tablets SmPC for treatment management.

Physician shall inform MAH of any pregnancy occurring in a subject exposed with the Cladribine 10 mg tablets during the course of the study by using separate paper data collection forms for pregnancy, independent if an AE was reported or not. Physician shall ensure that the case is followed up to the end of the pregnancy and provide all relevant documentation and a final report on the outcome including health status of a newborn to MAH.

In addition, pregnancy information has to be recorded in the relevant eCRF too.

## 12 STATISTICAL METHODOLOGY

Based on this part of the protocol, a statistical analysis plan (SAP) will be created. The statistical analysis plan will be processed and approved before closing the database. Possible changes in the evaluated parameters or in the methods of analysis against the protocol will be described and justified in SAP. The statistical analysis is performed in IBM SPSS software.

### 12.1 Sample Size

A sample size of 85 subjects will have more than 80% power to achieve a supposed ARR 0.14 (95 % CI: 0.12–0.17) using a 2-sided significance level of 0.05. Assuming a 15% drop-out rate, a total of 100 patients will be targeted for this study.

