	
performed using descriptive statistics: count (without missing), mean and its 95% confidence interval, standard deviation, median, minimum and maximum.
 
Interim analysis will be performed when all patients complete visit at month 25 or withdraw earlier.
 
A sample size of 85 subjects will have more than 80% power to achieve a supposed ARR 0.14 (95 % CI: 0.12–0.17) using a 2-sided significance level of 0.05. Assuming a 15% drop-out rate, a total of 100 patients will be targeted for this study.

Study Timelines:	
First patient first visit: April 2020
 
Last patient first visit: August 2021
 
End of data collection: October 2025
 
Enrolment period: 18 months
 
Participation of each patient will take approximately: 4 years (48 months). However, patients who postpone their therapy in year 2 due to low lymphocyte count up to 6 months (as per SmPC) are allowed to take part for up to 4.5 years in this case.

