## 5 STUDY DESIGN

### 5.1 Description of the study design

This is a non-interventional, multicentre, prospective study for patients with highly active relapsing MS for whom Cladribine 10 mg tablets therapy was indicated independently before enrolment to the study. It is planned to enrol about 100 patients in 12 sites specialized for MS treatment in Slovakia (for sample size consideration please see Section 12.1).

Eligible subjects will undergo all visits and procedures before and during the treatment as per local standards and Cladribine 10 mg tablets administration will be in accordance with approved SmPC. There is no assessment mandated per study protocol. Management of disease including administration of rescue therapy and visit schedule are fully at the treating physician's discretion. Data for the study will be extracted from medical charts and entered into the electronic Case Report Forms (eCRF). Study assessments schedule (Table 8-1: Flow chart) is approximate, all described assessments and events will be collected and finally statistician will analyse them within relevant window for respective visit. According to standard practice in Slovakia, patients treated by DMD visit their physician at MS centre at least once per year (as required by payers) but usually every 3 months.

To collect high quality adherence data, patients will be asked to bring used/partially used Cladribine 10 mg tablets packages to the next visit after dosing and physicians will record number of actually used tablets, if Cladribine 10 mg tablets are not administered in the participating site as per standard practice.

Patients will be followed up to 4 years after the first dose of Cladribine 10 mg tablets. Patients with low lymphocyte count to start Cladribine 10 mg tablets therapy after the first year are allowed to postpone second cycle up to 6 months until lymphocyte count recovers (as per SmPC) and therefore their participation may take up to 4.5 years.

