## 7 EVALUATION CRITERIA

### 7.1 Primary endpoint

- ARR at 48 months

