### 12.2 Data Analysis

Analysis of collected data is based on descriptive statistics including absolute and relative frequencies of discrete variables. Continuous variables are described by count (without missing), mean and its 95% confidence interval (CI), standard deviation, median, minimum, and maximum. Discrete variables are described by count (absolute frequency), and percentages (relative frequency).

Missing data will not be replaced.

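### Section 12.1 claims more than 80% power at two-sided 0.05 with no reference rate or test, so the power figure is undefined and cannot be reproduced from the printed numbers

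*Protocol*

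**What the plan says.** The sample-size justification is one claim, given in Section 12.1 and repeated under Statistical Considerations in the Protocol Summary: "A sample size of 85 subjects will have more than 80% power to achieve a supposed ARR 0.14 (95 % CI: 0.12–0.17"). Both places attach an alpha to this claim: "using a 2-sided significance level of 0.05". The inflation for drop-out follows: "Assuming a 15% drop-out rate, a total of 100 patients will be targeted for this study".

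The primary endpoint in Section 7.1 is "ARR at 48 months", measured in a single group. Section 5.1 gives the follow-up: "Patients will be followed up to 4 years after the first dose of Cladribine 10 mg tablets", or up to 4.5 years when the second course is postponed.

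For the primary endpoint the Protocol Summary plans an analysis "performed using descriptive statistics: count (without missing), mean and its 95% confidence interval, standard deviation, median, minimum and maximum". Section 12.2 says of the analysis in general: "Analysis of collected data is based on descriptive statistics including absolute and relative frequencies of discrete variables". None of these places gives a null or reference rate, a comparator or a hypothesis test. No source is given for the 0.14 or for its interval.

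**The concern.** Power is the probability that a stated test rejects a stated null value when a stated alternative is true. Section 12.1 supplies an alternative (0.14) and an alpha, but neither a null nor a test, and the planned analysis contains no test to which the alpha could apply. The bracketed interval is the only other number in the sentence. A reader will therefore try to use it either as the missing reference or as the precision that 85 patients give.

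What is at stake is how the result is read. Section 3 says the data are wanted by health authorities, payers and the local medical community. Such readers could take the study as powered at the 5% level for a claim that it never tests.

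**Working it through.** **Inputs.** From Section 12.1: 85 evaluable patients, 15% drop-out, ARR 0.14, interval 0.12–0.17, two-sided alpha 0.05. From Section 5.1: 4 years of follow-up. Assumptions not in the protocol: relapse counts are Poisson, the 85 patients complete 4 years, and drop-outs contribute no time. That gives 85 x 4 = 340 patient-years and 0.14 x 340 = 47.6 expected relapses. The premature-withdrawal visit collects relapses, so drop-outs will contribute some time; 100 x 4 = 400 patient-years is the upper bound at 4 years of follow-up.

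**Step 1, the drop-out step.** 85 / (1 − 0.15) = 100. This reproduces.

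**Step 2, power with a printed limit as the null.** Exact Poisson test, at most 0.025 in each tail, true ARR 0.14:

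| Null ARR | 340 patient-years | 400 patient-years |
|---|---|---|
| 0.12 | reject at ≥55 relapses; power 16% | reject at ≥63; power 19% |
| 0.17 | reject at ≤42 relapses; power 23% | reject at ≤51; power 28% |

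Neither limit gives anything near 80%. By the normal approximation, 80% power would need about 617 patients for a null of 0.12 and about 350 for 0.17, each followed for 4 years.

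**Step 3, which nulls would give 80%.** At 340 patient-years, exact power is 72% against 0.20 and 84% against 0.21. On the lower side it is 77% against 0.09 and 85% against 0.085. At 400 patient-years the thresholds move in slightly: 81% against 0.20 and 84% against 0.09. The protocol names none of these rates.

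**Step 4, the interval read as a precision target.** The Wald interval is 0.14 ± 1.96 x √(0.14 / patient-years).

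- 340 patient-years: 0.14 ± 0.040, or 0.100–0.180. The log-scale interval is 0.105–0.186.
- 400 patient-years: 0.14 ± 0.037, or 0.103–0.177.
- All 100 patients for 4.5 years (450 patient-years, an extreme case): 0.105–0.175.

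The width of 0.12–0.17 is 0.05, a half-width of 0.025. It requires 1.96² x 0.14 / 0.025² = 860 patient-years, or about 215 patients x 4 years. On the log scale it requires (2 x 1.96 / ln(0.17/0.12))² = 127 relapses, or about 905 patient-years and 226 patients.

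The same result in terms of the planned mean with its CI: a half-width of 0.025 from 85 patients needs a between-patient SD of 0.025 x √85 / 1.96 = 0.118. Poisson variation alone gives √(0.14/4) = 0.187.

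**Step 5, overdispersion.** With negative-binomial dispersion 1 (an assumption), the variance of a 4-year count is 0.56 + 0.56² = 0.874. The SE of the ARR is √(0.874/85)/4 = 0.0253, so the interval is 0.090–0.190.

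**Step 6, the closest reading.** The chance that the point estimate falls within 0.12–0.17 (41 to 57 relapses at 340 patient-years) is 77%. It is 82% at 400 patient-years, and 84% at 340 if the limits are widened to 0.115–0.175 for rounding.

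**The case against.** The strongest reply concerns the bracket. The interval is attached to the supposed rate, "supposed ARR 0.14 (95 % CI: 0.12–0.17"), and is not called a target width. It is asymmetric about 0.14, as a quoted estimate from earlier data might be, and Section 3 rests its efficacy rationale on earlier trials. A reader might infer that the protocol promises a CI of 0.12–0.17 which 85 patients cannot deliver. The text does not support that as a fact, because it never says what the interval is. This part of the objection stands, and the precision result holds only conditionally.

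A reader might also infer that the power figure is false or that 85 is the wrong number. Neither is shown. The power is undefined, and it would exceed 80% against a sufficiently distant reference rate on either side. The step from 85 to 100 is correct.

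Step 6 gives a reading that comes close to 80%. It does not rescue the sentence, because the chance that an estimate lands in a band is not the power of a test and makes no use of the two-sided 0.05.

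Finally, the study is descriptive. No success rule depends on the power figure, and the reported CI will show the precision actually achieved. That limits the consequence, but it does not make the sentence meaningful.

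**Conclusion.** The point holds in this form. The protocol attaches power and alpha to a descriptive analysis with no reference rate and no test, so the claim of more than 80% is undefined. Against the only candidate values printed, power is 16–19% (0.12) or 23–28% (0.17) over 340–400 patient-years. If 0.12–0.17 is a precision target, the planned exposure is about 40–47% of the 860 patient-years needed (340/860 and 400/860), and the expected interval is about 0.10–0.18. If it is an outside estimate, the defect there is an unsourced and ambiguous figure, while the power defect is unchanged.

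The figures rest on Poisson counts, a true ARR of 0.14 and 4 years of follow-up. Overdispersion would widen the interval. Endpoint, conduct and patient number are not affected.

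**What to change.** Keep the target of 100 patients. In Section 12.1 and in the Protocol Summary, delete the power and significance-level wording and state the expected precision. For example: at an ARR of 0.14, with 340 to 400 patient-years and Poisson counts, the 95% CI is expected to be about 0.10 to 0.18. Add that overdispersion would widen it, to about 0.09 to 0.19 if dispersion 1 is assumed, and label that value as an assumption.

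Say what the 0.12–0.17 interval is and give its source. Keep a power claim only if a reference ARR justified on clinical grounds and a test are named. The reference should not be chosen because it happens to give more than 80%.

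The cost is a wording change in two places, with no extra patients, visits or data. The drawback is that the stated precision becomes less favourable than the present text suggests.
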